Table 1. Study Schedule

Table 2. Laboratory Parameters

LIST OF FIGURES

Figure 1. Study Flow Sheet

LIST OF APPENDICES

None.

LIST OF ABBREVIATIONS AND DEFINITION OF TERMS

The following abbreviations and special terms are used in this study Clinical Study Protocol.

Abbreviation or special term	Explanation
ABI	Ankle brachial index
ASA	Acetylsalicylic acid; Aspirin
ANOVA	Analysis of Variance
BID	Twice a day
CVD	Cardiovascular disease
cP	Centipoise
DM	Diabetes mellitus
mg	Milligrams
MI	Myocardial infarction
OD	Oral dose
PAD	Peripheral artery disease
s ⁻¹	Inverse seconds; shear rate
WBV	Whole blood viscosity

1. INTRODUCTION

1.1 Background

Ticagrelor is a cyclopentyltriazolopyrimidine that has been shown to reduce significantly the rate of cardiovascular disease (CVD) events and death compared with clopidogrel in 18,624 patients having prior acute coronary syndrome [1]. The adenosine diphosphate receptor P2Y12 antagonist, clopidogrel 75 mg was more effective than aspirin 325 mg in reducing CVD events or death in a clinical trial of 19,185 patients with atherosclerosis, presenting with symptomatic peripheral artery disease (PAD), recent ischemic stroke or myocardial infarction (MI) [2]. In a pre-specified analysis of risk by the type of vascular events at entry, there was no reduction in MI, stroke or cardiovascular death rates in patients who entered the trial with an ischemic stroke or MI while there was a relative risk reduction of 23.8% (p=0.0028) in the group entering the trial with symptomatic PAD. The disproportionate event reduction in patients with PAD patients suggests that mechanisms other than atherosclerosis or thrombosis may contribute to CVD event reduction in these patients. Of the possible mechanisms, blood rheology is an important factor that influences macrovascular and microvascular flow in lower extremity arteries, and predicts CVD events in PAD patients.

1.2 Research hypothesis

Both aspirin-ticagrelor and ticagrelor monotherapy will be superior to aspirin monotherapy in the reduction of whole blood viscosity at the end of each 4 week treatment period.

1.3 Rationale for conducting this study

A previous study comparing 120 patients having intermittent claudication with normal age-matched controls found blood viscosity was significantly higher among claudicants ($p<0.001$) with the greatest difference in blood viscosity observed at lowest shears [3]. At high shear rates, patients with blood viscosity above 4.5 cP had mean claudication distance of 126 meters compared to 289 meters for patients with high-shear viscosity below that threshold. This report suggested the use of the term rheological claudication to describe approximately 25% of moderate to severe claudicants with hyperviscosity of blood having significantly worse prognoses.

In a random sample of 1,581 men and women 55 to 74 years of age with symptomatic or asymptomatic PAD, whole blood viscosity and fibrinogen were independently associated with peripheral arterial narrowing [4]. Plasma viscosity was also associated with claudication. The risk of claudication for patients in the upper quintile of plasma viscosity was 3.4 times greater than the risk for those in the lowest plasma viscosity quintile. The authors implicated blood rheological factors in the pathogenesis of lower limb ischemia in the general population.

The link between blood viscosity and ischemic heart disease events or strokes was reported in a study of a random population of 1,592 adults followed for a mean of 5 years: After adjustment for age and gender, both blood viscosity and hematocrit-corrected blood viscosity were higher in patients who experienced CVD events (myocardial infarction, angina pectoris, coronary revascularization or stroke) than in those who did not. The difference in blood viscosity between the two groups of patients was significant ($p=0.0003$) [5]. A number of outcome studies have demonstrated the risk of major CVD events increased with blood viscosity [6,7]. Stroke patients and those with stroke risk factors were shown to have chronically elevated blood viscosity relative to healthy controls [8].

A number of observational studies have reported increased blood viscosity in type 2 diabetics compared with nondiabetics. In an early clinical study comparing 16 diabetics with 16 age and gender-matched nondiabetic control subjects, mean blood viscosity at low shear rate was observed to be 26% higher in diabetics ($p<0.001$) [9]. A study of 38 male diabetics with and without retinopathy compared against 38 nondiabetics, matched for age and smoking habit, found low-shear blood viscosity levels were on average 13% higher in diabetics without retinopathy and 30% higher in those with retinopathy relative to control subjects [10]. These differences persisted after adjusting for hematocrit. A separate study of 64 diabetics and 61 matched nondiabetics reported similar results: elevated mean viscosity levels in diabetics compared with control subjects and the highest increases in diabetics with retinopathy or nephropathy [11].

Pharmacological therapies for reducing blood viscosity have been limited to clopidogrel [12], aspirin-dipyridamole [13] and in some studies pentoxifylline [14,15]. A reduction in blood viscosity has not been observed with either cilostazol [15] or ticlopidine [16]. In a double-blind, placebo-controlled study of 30 age and gender-matched patients with subclinical carotid or femoral atherosclerosis, clopidogrel was observed to reduce mean low-shear blood viscosity by 18% from baseline levels 3 weeks after administration (p<0.01) [12].

1.4 Benefit/risk and ethical assessment

The cross-over study design exposes each randomized group to each of the three treatments, thus reducing treatment bias. Aspirin monotherapy for treatment of PAD is technically an off-label use, however, it remains a Class I recommendation by the ACCF/AHA Task Force on Practice Guidelines when given in daily doses of 75 to 325 mg as a safe and effective antiplatelet therapy to reduce risk of CVD events in those with symptomatic lower extremity PAD [17]. Patients should be counseled on the importance of not taking aspirin outside of the study because doses greater than 100 mg/day can reduce the efficacy of ticagrelor [18]. When possible, if ticagrelor treatment results in bleeding, the bleeding should be managed without stopping therapy as increased risk of CVD events can occur. Also, patients with history of hyperuricemia, gouty arthritis, hepatic impairment, and renal impairment should be monitored closely if taking ticagrelor.

2. STUDY OBJECTIVES

2.1 Primary objective

- (1) Compare the effect of aspirin-ticagrelor with aspirin in a double blind, randomized, cross-over study design (weeks 1-4, weeks 6-10, and weeks 12-16) on blood viscosity at both low (5 s^{-1}) and high (300 s^{-1}) shear rates at the end of each 4-week treatment period.
- (2) Compare the effect of ticagrelor monotherapy with aspirin in a double blind, randomized, cross-over study design (weeks 1-4, weeks 6-10, and weeks 12-16) on blood viscosity at both low (5 s^{-1}) and high (300 s^{-1}) at the end of each 4-week treatment.

2.2 Secondary objectives

- (1) Determine whether there are differences in low and high shear rate dependent viscosity with treatment by ticagrelor alone and combination aspirin-ticagrelor.
- (2) Investigate the effect of the treatment on peripheral arterial blood flow using pulse volume recordings, ankle brachial index, toe pressures and laser flow Doppler (a new emerging technique capable of measuring the velocity of flow and number of cells in the vessel, providing a normalized measure of microcirculatory flow (velocity of flow x number of cells/backscatter)

2.3 Safety objective

This study is not designed to compare safety between treatments.

2.4 Exploratory objectives

Not applicable.

3. STUDY PLAN AND PROCEDURES

3.1 Overall study design and flow chart

The proposed, double-blind, placebo-controlled, cross-over design study examines and compares the effects of low-dose aspirin, combination aspirin-ticagrelor, and ticagrelor monotherapy on blood viscosity in type 2 diabetes patients with symptomatic PAD who are 18 years of age or older. Study participants will be randomized into 3 groups, and each group will receive each of 3 treatments in the cross-over study. Subjects will be eligible if they have ankle-brachial index less than or equal to 0.85, or if a patient's blood vessels are calcified, patients will have toe-brachial index less than or equal to 0.6 performed using continuous-wave Doppler. Pulse volume recordings will be simultaneously obtained at the level of the ankle, metatarsal and toe bilaterally (Parks Flolab, Parks Medical Electronics, Aloha, OR) according to standard protocol as well as Laser flow Doppler (Perimed Periflux 5000, Perimed AB, Sweden). Subjects will be excluded for planned revascularization or amputation, as well as for known hypersensitivity or allergic reactions to aspirin, bleeding disorders, history of intracranial hemorrhage, and those considered to be at risk of hemorrhagic events will also be excluded from the study. Aspirin 81 mg has been shown to have no significant effect on blood viscosity in healthy individuals [13], and will be used as background therapy prior to randomization; this treatment will serve as comparison for control.

[figure not shown]
After 2 weeks run-in treatment with aspirin 81 mg daily, patients will be randomized to one of 3 arms (ticagrelor placebo and aspirin 81 mg (Group A), ticagrelor and aspirin 81 mg (Group B), or ticagrelor monotherapy with aspirin placebo (Group C)) and treated for 4 weeks. At this initial visit and every visit thereafter, laboratory assessments will be performed, including whole blood viscosity, complete blood count (CBC), fibrinogen, globulins, lipid profile, ankle/toe brachial index, and pulse volume recording (PVR). Vital signs will also be assessed at each visit. At the end of 4 weeks treatment, all 3 groups will receive aspirin 81 mg for 2 weeks to reestablish baseline values. After the 2-week washout, the ticagrelor placebo and aspirin 81 mg treatment group (Group A) will be treated with aspirin 81 mg daily and ticagrelor; the aspirin 81 mg daily and ticagrelor treatment group (Group B) will be treated with ticagrelor monotherapy; and, the ticagrelor monotherapy group (Group C) will be treated with ticagrelor placebo and aspirin 81 mg daily for 4 weeks. After the end of 4 weeks treatment, again, all 3 groups will receive aspirin 81 mg for 2 more weeks to re-establish baselines. After this 2-week washout period, the third and final treatment will be for 4 weeks as follows: ticagrelor monotherapy for Group A, ticagrelor placebo and aspirin 81 mg for Group B, and ticagrelor with aspirin 81 mg for Group C. After randomization, the time-window beginning with Visit 1 and for

The 3 treatment groups will receive:

1. Group A: Aspirin 81 mg daily and ticagrelor placebo twice daily
2. Group B: Aspirin 81 mg daily and ticagrelor 90 mg twice daily
3. Group C: Aspirin placebo daily and ticagrelor 90 mg twice daily

Each treatment group will receive all 3 of the above treatments in this cross-over study.

Figure 1. Study Flow Sheet

^a Laboratory Assessments: whole blood viscosity, CBC, fibrinogen, globulins, lipid profile, ankle/toe brachial index, pulse volume recording (PVR).

^b Time Window is ± 7 days.

^c ABI with exercise will be done at screening to identify subjects with claudication symptoms who may have resting ABIs > 0.85 .

3.2 Rationale for study design, doses and control groups

A previous study comparing 120 patients having intermittent claudication with normal age-matched controls found blood viscosity was significantly higher among claudicants ($p < 0.001$) with the greatest difference in blood viscosity observed at lowest shears [3]. At high shear rates, patients with blood viscosity above 4.5 cP had mean claudication distance of 126 meters compared to 289 meters for patients with high-shear viscosity below that threshold. This report suggested the use of the term rheological claudication to describe approximately 25% of moderate to severe claudicants with hyperviscosity of blood having significantly worse prognoses.

In a random sample of 1,581 men and women 55 to 74 years of age with symptomatic or asymptomatic PAD, whole blood viscosity and fibrinogen were independently associated with peripheral arterial narrowing [4]. Plasma viscosity was also associated with claudication. The risk of claudication for patients in the upper quintile of plasma viscosity was 3.4 times greater than the risk for those in the lowest plasma viscosity quintile. The authors implicated blood rheological factors in the pathogenesis of lower limb ischemia in the general population.

The link between blood viscosity and ischemic heart disease events or strokes was reported in a study of a random population of 1,592 adults followed for a mean of 5 years: After adjustment for age and gender, both blood viscosity and hematocrit-corrected blood viscosity were higher in patients who experienced CVD events (myocardial infarction, angina pectoris, coronary revascularization or stroke) than in those who did not. The difference in blood viscosity between the two groups of patients was significant ($p=0.0003$) [5]. A number of outcome studies have demonstrated the risk of major CVD events increased with blood viscosity [6,7]. Stroke patients and those with stroke risk factors were shown to have chronically elevated blood viscosity relative to healthy controls [8].

A number of observational studies have reported increased blood viscosity in type 2 diabetics compared with nondiabetics. In an early clinical study comparing 16 diabetics with 16 age and gender-matched nondiabetic control subjects, mean blood viscosity at low shear rate was observed to be 26% higher in diabetics ($p<0.001$) [9]. A study of 38 male diabetics with and without retinopathy compared against 38 nondiabetics, matched for age and smoking habit, found low-shear blood viscosity levels were on average 13% higher in diabetics without retinopathy and 30% higher in those with retinopathy relative to control subjects [10]. These differences persisted after adjusting for hematocrit. A separate study of 64 diabetics and 61 matched nondiabetics reported similar results: elevated mean viscosity levels in diabetics compared with control subjects and the highest increases in diabetics with retinopathy or nephropathy [11].

Pharmacological therapies for reducing blood viscosity have been limited to clopidogrel [12], aspirin-dipyridamole [13] and in some studies pentoxifylline [14,15]. A reduction in blood viscosity has not been observed with either cilostazol [15] or ticlopidine [16]. In a double-blind, placebo-controlled study of 30 age and gender-matched patients with subclinical carotid or femoral atherosclerosis, clopidogrel was observed to reduce mean low-shear blood viscosity by 18% from baseline levels 3 weeks after administration ($p<0.01$) [12].

4. SUBJECT SELECTION CRITERIA

4.1 Inclusion criteria

For inclusion in the study subjects should fulfill the following criteria:

1. Provision of informed consent prior to any study specific procedures
2. Subject is willing to comply with the requirements of the study protocol

3. Male or female \geq 18 years of age
4. Type 2 diabetes mellitus
5. Symptomatic PAD
6. Ankle-brachial index \leq 0.85 or calcified blood vessels with toe-brachial index \leq 0.6 and/or abnormal post-exercise ankle-brachial index.⁷ Prior surgical or percutaneous intervention of the peripheral arteries \geq -3 months with non-drug eluting stent placement and \geq 12 months for those with drug-eluting stents previously with a residual stenoses of \geq 50% in a non-dilated artery.
8. Subject has hypersensitivity or allergic reactions to clopidogrel

4.2 **Exclusion criteria**

Subjects should not enter the study if any of the following exclusion criteria are fulfilled:

1. Type I diabetes, poorly controlled diabetes (HbA1c \geq ~~8.5~~[±]09.5%), newly diagnosed type 2 diabetes (within 6 months of randomization), or laboratory evidence of diabetes during screening (fasting serum glucose \geq 126 mg/dL [7.0 mmol/L] or HbA1c \geq 6.5%) without prior diagnosis of diabetes
2. Uncontrolled hypertension defined as sitting systolic blood pressure (SBP) $>$ 180 mmHg or diastolic BP (DBP) $>$ 100 mmHg
3. NYHA III or IV heart failure, or last known left ventricular ejection fraction (LVEF) \leq 30%
4. Subject has a hypersensitivity or allergic reactions to ticagrelor
5. Subject has a hypersensitivity or allergic reactions to aspirin
6. Subject who has known sensitivity to any of the products or components to be administered during dosing or procedures
7. Need for chronic oral anticoagulation therapy (e.g. cilostazole) or chronic low-molecular-weight heparin or long-term treatment with fondaparinux
8. Planned revascularization (surgical or endovascular) in any vascular territory during the duration of the study
9. Planned amputation due to PAD within the duration of the study or amputation due to PAD within the last 30 days
10. Subjects who have suffered a stroke in the last 3 months

11. Dementia likely to jeopardize understanding of information pertinent to study conduct or compliance to study procedures
12. Subject has a history of severe liver disease (e.g. ascites and/or clinical signs of coagulopathy) or obstructive liver disease [(e.g. primary biliary cirrhosis or end-stage renal disease (eGFR \leq 30 mL/min/m²)]
13. A known bleeding diathesis, haemostatic or coagulation disorder, or systemic bleeding, whether resolved or ongoing
14. History of previous intracranial bleed at any time, gastrointestinal bleed within the past 6 months, or major surgery within the past 3 months of screening (if the surgical wound is judged to be associated with an increased risk of bleeding)
15. Considered at risk of hemorrhagic events
16. Subject who has not been on stable lipid lowering therapy in the last 3 months prior to LDL-C screening [e.g. red yeast rice, > 200mg/day niacin, or prescription lipid-regulating drugs (e.g. fibrates and derivatives, statins, ezetimibe) other than bile-acid sequestering resin, or stanols/plant stanols and stanol esters
17. Treatment in the last 3 months prior to LDL-C screening with any of the following drugs: systemic cyclosporine, systemic steroids (e.g. IV, intramuscular [IM], or PO) (Note: hormone replacement therapy is permitted), Oral vitamin A derivatives and retinol derivatives for the treatment of dermatologic conditions (e.g. Accutane); (Note: Vitamin A in a multivitamin preparation, as well as topical retinoid and retinol creams are permitted)
18. Initiation of prescription triglyceride lowering therapy (e.g. Lovaza) which is not stable within 6 weeks of screening
19. Subject has acute infection (e.g. bacterial, fungal) within the previous 6 weeks prior to screening (Note: subjects with a viral infection such as the common cold are not excluded)
20. Subject has anemia (hemoglobin \leq 8.5 g/dL) that requires a potential blood transfusion within 6 weeks of screening
21. Subject has given blood or received a blood transfusion within the previous 3 months prior to screening
22. Subject has polycythemia vera or any hyperviscosity syndrome
23. Subjects with Waldenstrom's macroglobulinemia who have an increased risk of hyperviscosity syndrome

24. Female subject who has either (1) not used at least 1 highly effective method of contraception for at least 1 month prior to screening or (2) is not willing to use such a method during treatment and for an additional 15 weeks after the end of treatment, unless the subject is sterilized or postmenopausal. Menopause is defined as: 12 months of spontaneous and continuous amenorrhea in a female \geq 55 years old or 12 months of spontaneous and continuous amenorrhea with a follicle-stimulating hormone (FSH) level $>$ 40 IU/L (or according to the definition of "postmenopausal range" for the laboratory involved) in a female $<$ 55 years old unless the subject has undergone bilateral oophorectomy. Highly effective methods of birth control include: not having intercourse or using birth control methods that work at least 99% of the time when used correctly and include: birth control pills, shots, implants, or patches, intrauterine devices (IUDs), tubal ligation/occlusion, sexual activity with a male partner who has had a vasectomy, condom or occlusive cap (diaphragm or cervical/vault caps) used with spermicide
25. Subject is pregnant or breast-feeding, or planning to become pregnant during treatment and/or within 15 weeks after the end of treatment
26. Subject who is likely to not be available to complete all protocol-required study visits or procedures, and/or to comply with all required study procedures (e.g. blood collection procedures to ensure subject safety to the best of the subject and investigator's knowledge)
27. History or evidence of any other clinically significant disorder, condition or disease (with the exception of those outline above) that, in the opinion of the Investigator or Sponsor, if consulted, would pose a risk to subject safety or interferes with the study evaluation, procedures or completion (e.g. active malignancy other than squamous cell or basal cell skin cancer, use of strong or moderate CYP2C19 inhibitors, long-term concomitant treatment with non-steroidal anti-inflammatory drugs [NSAIDs])
28. Unreliability as a study participant based on the Investigator's (or designee's) knowledge of the subject (e.g. alcohol or other drug abuse, inability or unwillingness to adhere to the protocol, or psychosis)
29. Currently enrolled in another investigational device or drug study, or less than 30 days since ending another investigational device or drug study(s), or receiving other investigational agent(s)
30. Family members or employees of the investigator or study centers involved in the study

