5.5.4 Labeling

Labeling for 4 treatments (aspirin 81 mg daily, aspirin placebo daily, ticagrelor 90 mg twice daily, and ticagrelor placebo twice daily) will be coded.

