6.2 Data collection at enrollment and follow-up

6.2.1 Enrollment procedures

Potential subjects will answer questions and these responses will be recorded on the CRF. Subjects will be asked if they are pregnant; pregnant subjects will not qualify for enrollment in this study. Qualifying subjects will be requested to enroll into the study. Subjects satisfying all inclusion criteria and without any reason for exclusion will be eligible for the study. Subjects not fulfilling the requirements are not eligible and will be replaced. The following data will be recorded on the subject's CRF: demographics, CVD risk factors (including smoker/non-smoker, hypertension, diet, physical activity), clinical history, vital signs, and medications. Those subjects who sign the informed consent and who pass the initial screening will be administered aspirin 81 mg by mouth once daily for 2 weeks.

After 2 weeks run-in treatment with aspirin 81 mg daily, patients will be randomized to one of 3 arms (ticagrelor placebo and aspirin 81 mg (Group A), ticagrelor and aspirin 81 mg (Group B), or ticagrelor monotherapy with aspirin placebo (Group C)) and treated for 4 weeks. Laboratory assessments will be performed, including whole blood viscosity, complete blood count (CBC), fibrinogen, globulins, lipid profile, ankle/toe brachial index, and pulse volume recording (PVR). Some of the laboratory samples will be stored in a -70°C freezer for future assessments and genetic testing. Vital signs will also be assessed at each visit.

Any adverse events (AEs) will be properly recorded on the CRF, and any Serious Adverse Events (SAEs) will be recorded on SAE forms (MEDWATCH 3500A Form) and the AE form of the CRF, and will be reported to the Sponsor. Any AE not resolved or not resolved with sequelae within thirty minutes after the scheduled blood draw will be followed until such resolution occurs, and this resolution will be noted on the CRF.

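### Section 4.1 item 8 makes clopidogrel hypersensitivity a condition of entry for every subject, although clopidogrel is not a study drug and no reason is given

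*Combined protocol and SAP*

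**What the plan says.** Section 4.1 opens its list with "For inclusion in the study subjects should fulfill the following criteria". The list ends with item 8, "Subject has hypersensitivity or allergic reactions to clopidogrel".

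Section 6.2.1 gives the rule for combining the criteria: "Subjects satisfying all inclusion criteria and without any reason for exclusion will be eligible for the study". It adds the consequence of failing one: "Subjects not fulfilling the requirements are not eligible and will be replaced".

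Section 4.2 has two items in almost the same words, placed among the exclusions: item 4, "Subject has a hypersensitivity or allergic reactions to ticagrelor", and item 5, "Subject has a hypersensitivity or allergic reactions to aspirin". Both name a drug given in the trial.

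Section 3.1 describes the population as adults with type 2 diabetes and symptomatic PAD who meet an ankle-brachial or toe-brachial threshold. Among its reasons for exclusion it gives "as well as for known hypersensitivity or allergic reactions to aspirin". It does not mention clopidogrel.

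**The concern.** An inclusion criterion is a condition each subject must have. Item 8 asks for an allergy to a drug that nobody in this trial receives, and the protocol does not say why. The near-identical items for the drugs that are given sit on the other side of the eligibility line.

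What is at stake is who may enrol and to whom the result applies. Followed to the letter, the trial studies only clopidogrel-hypersensitive patients, a population that neither the research hypothesis (Section 1.2) nor the objectives (Section 2) mentions. Not followed, sites enrol people whom the written protocol calls ineligible. Section 6.5 refers to three sites, and nothing in the text ensures that they would read the item alike.

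**Working it through.** No plan figure depends on this item, so there is nothing to recompute. The check is a comparison of the text and a count.

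**1. Is item 8 current text and in the inclusion list?** Yes. Nearby text shows signs of editing: items 6 and 7 run together, and the HbA1c limit in exclusion 1 carries residue of a change. Item 8, however, has its own number and line and no deletion mark.

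**2. Is it binding?** The lead-in to Section 4.1 is worded as an expectation, which alone might leave some room. Section 6.2.1 removes it by requiring all inclusion criteria and declaring anyone who falls short ineligible. Nothing links item 8 to the other items as an alternative.

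**3. Is clopidogrel a study treatment?**

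| Place | Items listed | Of which clopidogrel |
|---|---|---|
| Section 5.5.1, investigational products | 2 (ticagrelor, aspirin) | 0 |
| Section 5.5.2, regimens | 3 | 0 |
| Section 5.5.4, labelled treatments | 4 (two active, two placebo) | 0 |

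**4. Does any other text explain the item?** Clopidogrel is named in six places:
- Sections 1.1, 1.3 and 3.2: literature background.
- Section 4.1: item 8 itself.
- Section 12.3: the source of the 2.0 cP reduction assumed for the sample size.
- Section 14: the reference list.

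Only one of the six concerns eligibility, and none gives a reason for the restriction.

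**5. How are comparable items placed?** Three items in Sections 4.1 and 4.2 name a drug and hypersensitivity to it. The 2 that name a study drug are exclusions; the 1 that names a drug not given is an inclusion. This pattern is consistent with a misplaced or mistyped item, but does not prove it.

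**6. What follows under each reading?**
- *Literal requirement:* all 90 patients to be randomised (Section 12.3) must be clopidogrel-hypersensitive. Section 6.2.1 decides eligibility before the 2-week run-in, so the effect would appear as screening failures.
- *Permissive, meaning that such patients may enter:* patients without the hypersensitivity are correctly enrolled, but no wording says so.
- *Misplaced exclusion:* clopidogrel-hypersensitive patients would be kept out, the opposite of the present text.
- *Deliberate restriction to patients who cannot take clopidogrel:* the population is narrower than the one in Section 3.1, and no section says so.

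These readings lead to different enrolled populations. The documents do not decide between them.

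**7. Can the size be calculated?** No. The documents give no prevalence of clopidogrel hypersensitivity, and the sample size (72 patients required, 90 randomised) does not use this criterion.

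**The case against.** The strongest objection is that the end of the list may never have been meant as universal conditions. Item 7, on earlier surgical or percutaneous intervention, also reads oddly if every subject must satisfy it, and Section 3.1 has no such requirement. Two such items in a row suggest permissive or conditional entries. This is plausible as intent, and it shows that item 7 needs the same clarification. It does not rescue item 8: no wording marks it as permissive, and Section 6.2.1 applies to all the criteria.

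A second objection is that the contradiction with Section 3.1 is weak, because that section is a summary that leaves out many criteria. This is fair, and its silence is supporting evidence only. The finding rests on item 8, the rule in Section 6.2.1 and the absence of any rationale.

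Third, an intended restriction is conceivable. Section 1.1 reports clopidogrel as more effective than aspirin in symptomatic PAD, so a trial with an aspirin-only treatment period might be limited to patients who cannot take clopidogrel. That is inference; the protocol does not say it. If it is the reason, it belongs in the text.

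Last, the consequences under Section 5.3 (replacement of incorrectly enrolled subjects) and Section 5.9 (withdrawal of those found not to meet requirements) arise only if sites ignore item 8 and it is later enforced. That scenario is hypothetical, and the conclusion does not depend on it.

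**Conclusion.** The concern holds and needs correcting. As written, the protocol admits only patients with hypersensitivity or allergy to a drug that is not part of the trial, gives no reason, and elsewhere describes a population without that condition. The conclusion rests on two things: item 8 being current text, and Section 6.2.1 meaning what it says about all criteria. It assumes no prevalence and does not presume what the sponsor intended.

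The consequence is categorical rather than numerical: the enrolled population is either the one in Section 3.1 or a restricted subset of it, and the reader cannot tell which. The treatments, the blinding and the within-subject comparisons of viscosity are unaffected.

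**What to change.** The sponsor should state the purpose of item 8 and amend Sections 3.1, 4.1, 4.2 and 6.2.1 so that they agree.

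- If the Section 3.1 population is intended, item 8 must not stand among the conditions every subject has to meet. Any permissive meaning should be written as such. Cost: a text amendment, with no extra patients or procedures.
- If a clopidogrel-hypersensitive population is intended, Section 3.1 should say so and give the reason, and the eventual report should limit its conclusions accordingly. Cost: the same amendment, plus a check that 90 such patients can be recruited.

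The same amendment should say whether item 7 is required of everyone or applies only to patients with an earlier intervention. If anyone has already been enrolled without meeting item 8, the amendment should state how they are treated under Sections 5.3 and 5.9 and in the analysis; Section 12.1 is silent on subjects enrolled against a criterion.
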